7.4.2 Dose Delay Criteria

Delay administration of nivolumab if any of the delay criteria in [Table 7.4.1-1](#) and [Section 7.4.1](#) are met. Nivolumab administration should also be delayed for the following:

- For participants with HCC:
 - Any Grade 3 drug-related laboratory abnormality with the following exceptions:
 - ◆ Grade 3 amylase or lipase abnormalities that are not associated with symptoms or clinical manifestations of pancreatitis do not require a dose delay.
 - Dose delay for changes in AST or ALT as follows:
 - ◆ If a participant has a baseline AST or ALT that is within normal limits, delay dosing for drug-related Grade ≥ 2 toxicity (2 grade shift)
 - ◆ If a participant has baseline AST or ALT within the Grade 1 toxicity range, delay dosing for drug-related Grade ≥ 3 toxicity (2 grade shift)
 - ◆ If a participant has baseline AST or ALT $>$ within the Grade 2 toxicity range, delay dosing for a 2-fold drug-related increase in AST or ALT or for AST or ALT values $8 \times$ ULN (whichever is lower)
- Any AE, laboratory abnormality, or intercurrent illness which, in the judgment of the investigator, warrants delaying the dose of study medication.

Participants who require delay of nivolumab should be re-evaluated weekly or more frequently if clinically indicated and resume nivolumab dosing when re-treatment criteria are met. For participants with HCC, it is recommended to monitor elevations in AST or ALT approximately every 3 days till levels peak or begin to decline.

If dosing is resumed after a delay, study treatment may be resumed as soon as possible after the criteria to resume treatment are met (see [Section 7.4.3](#)).

7.4.3 Criteria to Resume Treatment

Participants may resume treatment with study drug if they have completed AE management (ie corticosteroid taper) or are on ≤ 10 mg prednisone or equivalent, and meet the requirements per [Table 7.4.1-1](#).

Prior to re-initiating treatment in a participant with a dosing delay lasting > 6 weeks, the Medical Monitor (or designee) must be consulted. Continue tumor assessments per protocol even if dosing is delayed. Continue periodic study visits to assess safety and laboratory studies every 6 weeks in Parts A-D or every 2 weeks in Part E or more frequently if clinically indicated during such dosing delays.

- Participants with HCC
 - Participants with baseline Grade 1 AST, ALT, or total bilirubin who require dose delays for reasons other than a drug-related hepatic event may resume treatment in the presence of Grade 2 AST, ALT, or total bilirubin.
 - Participants who require dose delays for drug-related elevations in AST, ALT, or total bilirubin may resume treatment when these values have returned to their baseline CTCAE Grade or normal, provided the criteria for permanent discontinuation are not met ([Section 8.1.1](#)).

Drug-related pulmonary toxicity, diarrhea, or colitis must have resolved to baseline before treatment is resumed. Participants with persistent Grade 1 pneumonitis after completion of a steroid taper over at least 1 month may be eligible for retreatment if discussed with and approved by BMS medical monitor or designee.

Participants with drug-related endocrinopathies adequately controlled with only physiologic hormone replacement may resume treatment after consultation with the BMS medical monitor or designee.

For all AEs, corticosteroid therapy must be tapered to prednisone 10 mg/day or equivalent prior to resuming study therapy unless being used as adrenal replacement steroid therapy.

If the criteria to resume treatment are met, the participant should restart treatment at the next scheduled timepoint per protocol. If treatment is delayed > 6 weeks from the last dose, the participant must be permanently discontinued from study therapy, except as specified in Section 8.1.1 and [Section 8.1.2](#). Please see also [Appendix 6](#) (Management Algorithms) for guidance on appropriate management and follow-up of adverse events. For hepatic AE management, see [Section 7.4.4.2](#).

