7.4 Dosage Modification

7.4.1 *Dose Modifications*

Dose delay criteria apply for all drug-related adverse events (regardless of whether the event is attributed to nivolumab). Delay administration of nivolumab if any of the delay criteria in [Table 7.4.1-1](#) are met. Delay nivolumab dosing for any AE, laboratory abnormality, or intercurrent illness which, in the judgment of the investigator, warrants delaying the dose of study medication.

For participants who require delay of nivolumab, re-evaluate weekly, or more frequently, if clinically indicated and resume dosing when criteria to resume treatment are met (see [Section 7.4.3](#)). Continue tumor assessments per protocol even if dosing is delayed.

Table 7.4.1-1: Adverse Event Criteria for Delay, Resume, and Discontinue of Subcutaneous Nivolumab with or without rHuPH20

Drug-related AE per CTCAE V5	Severity	Action Taken	Clarifications, Exceptions, and Resume Criteria
Gastrointestinal			
Colitis or Diarrhea	Grade 2	Delay dose	Dosing may resume when AE resolves to baseline
	Grade 3	Delay dose	Dosing may resume when AE resolves to baseline
	Grade 4	Permanently discontinue	
Renal			
Serum Creatinine Increased	Grade 2 or 3	Delay dose	Dosing may resume when AE resolves to Grade \leq 1 or baseline value
	Grade 4	Permanently discontinue	
Pulmonary			
Pneumonitis	Grade 2	Delay dose	Dosing may resume after pneumonitis has resolved to \leq Grade 1
	Grade 3 or 4	Permanently discontinue	

Table 7.4.1-1: Adverse Event Criteria for Delay, Resume, and Discontinue of Subcutaneous Nivolumab with or without rHuPH20

Drug-related AE per CTCAE V5	Severity	Action Taken	Clarifications, Exceptions, and Resume Criteria
Hepatic			
AST, ALT, or T.bili increased (For non-HCC participants; For HCC participants, see Section 7.4.2 and Section 7.4.3)	AST or ALT $> 3\times$ and $\leq 5\times$ upper limit of normal (ULN) or T.Bili $> 1.5\times$ and $\leq 3\times$ ULN, regardless of baseline value	Delay dose	Dosing may resume when laboratory values return to baseline.

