	AST or ALT $> 5\times$ ULN or T. bili $> 3\times$ ULN, regardless of baseline value	Delay dose or permanently discontinue	In most cases of AST or ALT $> 5\times$ ULN, study treatment will be permanently discontinued. If the investigator determines a possible favorable benefit/risk ratio that warrants continuation of study treatment, a discussion between the investigator and the Medical Monitor/ designee must occur and approval from Medical Monitor prior to resuming therapy.
	Concurrent AST or ALT $> 3\times$ ULN and T.bili $> 2\times$ ULN, regardless of baseline value	Permanently discontinue	
Endocrinopathy			
Adrenal Insufficiency	Grade 2 adrenal insufficiency	Delay dose	Dosing may resume after adequately controlled with hormone replacement
	Grade 3 or 4 adrenal insufficiency or adrenal crisis	Delay dose or permanently discontinue	Mandatory discussion with and approval from the Medical Monitor needed prior to resuming therapy. If adrenal insufficiency resolves or is adequately controlled with physiologic hormone replacement, participant may not require discontinuation of study drug

Table 7.4.1-1: Adverse Event Criteria for Delay, Resume, and Discontinue of Subcutaneous Nivolumab with or without rHuPH20

Drug-related AE per CTCAE V5	Severity	Action Taken	Clarifications, Exceptions, and Resume Criteria
Hyperglycemia	Hyperglycemia requiring initiation or change in daily management (Grade 2 or 3)	Delay dose	Dosing may resume if hyperglycemia resolves to Grade ≤ 1 or baseline value, or is adequately controlled with glucose-controlling agents
	Grade 4	Delay dose or permanently discontinue	Mandatory discussion with and approval from the Medical Monitor needed prior to resuming therapy. If hyperglycemia resolves, or is adequately controlled with glucose-controlling agents, participant may not require discontinuation of study drug
Hypophysitis/Hypopituitarism	Symptomatic Grade 1-3 that is also associated with corresponding abnormal lab and/or pituitary scan	Delay dose	Dosing may resume if endocrinopathy resolves to be asymptomatic, or is adequately controlled with only physiologic hormone replacement
	Grade 4	Delay dose or permanently discontinue	Mandatory discussion with and approval from the Medical Monitor needed prior to resuming therapy. If endocrinopathy resolves or is adequately controlled with physiologic hormone replacement, participant may not require discontinuation of study drug

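### The Grade 2 pneumonitis row of Table 7.4.1-1 lets dosing resume at Grade 1 or lower, while Section 7.4.3 requires baseline, or persistent Grade 1 only after a completed taper and Medical Monitor approval

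*Combined protocol and SAP*

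**What the plan says.** Two places in the protocol set the rule for restarting nivolumab after drug-related lung toxicity.

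- **Table 7.4.1-1**, titled "Adverse Event Criteria for Delay, Resume, and Discontinue of Subcutaneous Nivolumab with or without rHuPH20", has a row for Grade 2 pneumonitis. The dose is delayed, and "Dosing may resume after pneumonitis has resolved to" Grade 1 or lower. The cell has no other condition. Grade 3 or 4 means permanent discontinuation, so Grade 2 is the only pneumonitis row with a route back to treatment.
- **Section 7.4.3 (Criteria to Resume Treatment)** states: "Drug-related pulmonary toxicity, diarrhea, or colitis must have resolved to baseline before treatment is resumed". The next sentence gives the exception: "Participants with persistent Grade 1 pneumonitis after completion of a steroid taper over at least 1 month may be eligible for retreatment". The exception also depends on the sponsor's agreement; it holds only "if discussed with and approved by BMS medical monitor or designee".

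Section 7.4.3 opens with a general rule: "Participants may resume treatment with study drug if they have completed AE management (ie corticosteroid taper) or are on" at most 10 mg prednisone or equivalent, and if they meet the requirements of Table 7.4.1-1. That sentence does not mention the further conditions later in the section.

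Sections 7.4.1, 7.4.2 and 8.1.3 each refer the reader to Section 7.4.3 for the criteria to resume.

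**The concern.** This is an operative re-dosing rule for a toxicity where rechallenge needs care. The table states a grade threshold, while the text states return to the participant's own baseline with a narrow, supervised exception. Nothing says which governs if they differ.

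The row can be mistaken for the whole rule. The table presents itself as containing resume criteria, and the opening sentence of Section 7.4.3 points back to it as if meeting the table were enough once steroids are dealt with. At stake is whether a participant with residual Grade 1 pneumonitis restarts without a finished taper of at least 1 month and without the Medical Monitor's approval. Those are safeguards that the sponsor itself wrote.

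**Working it through.** No arithmetic applies. The check sets the two rules side by side and asks where they give different answers.

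**1. Cases after a drug-related Grade 2 pneumonitis.** In each case the participant already meets the general steroid condition of Section 7.4.3 (taper done, or at most 10 mg prednisone or equivalent).

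| Baseline | Current state | Table row with opening sentence of 7.4.3 | Pulmonary sentences of 7.4.3 |
|---|---|---|---|
| None | Fully resolved | Resume | Resume |
| Grade 1 | Grade 1 | Resume | Resume (baseline reached) |
| None | Grade 1, taper of at least 1 month finished, Medical Monitor approves | Resume | Resume (exception met) |
| None | Grade 1, still on 10 mg prednisone or less | Resume | Do not resume |
| None | Grade 1, taper finished, no Medical Monitor approval | Resume | Do not resume |

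The rules differ only when pneumonitis was absent at baseline, Grade 1 persists, and the exception is not met.

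**2. Other rows within reach of the same Section 7.4.3 sentence.** It covers pulmonary toxicity, diarrhea and colitis. The rows that permit resumption are:

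- colitis or diarrhea, Grade 2: "Dosing may resume when AE resolves to baseline", which agrees with 7.4.3;
- colitis or diarrhea, Grade 3: same wording, which agrees;
- pneumonitis, Grade 2: Grade 1 or lower, which is looser;
- other drug-related AE, Grade 2 non-skin (fatigue excepted): Grade 1 or lower, or baseline; looser when the event is pulmonary;
- other drug-related AE, first Grade 3 lasting 7 days or less: same criterion; looser when the event is pulmonary.

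So of five rows, two agree, one is looser, and two are looser for pulmonary events other than pneumonitis. For those other pulmonary events Section 7.4.3 offers no Grade 1 exception, since the exception names pneumonitis only.

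**3. Does the table show extra steps where they are wanted?** Often. Six rows name a Medical Monitor step in the cell: AST or ALT above 5 times ULN or bilirubin above 3 times ULN; adrenal insufficiency Grade 3 or 4; Grade 4 hyperglycemia; Grade 4 hypophysitis; Grade 4 thyroid events; and SARS-CoV-2 infection. The four endocrine rows among them use the words "Mandatory discussion with and approval from the Medical Monitor needed prior to resuming therapy". The pneumonitis row has no such step and no pointer to Section 7.4.3.

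**The case against.** The strongest reply is that the documents already answer the question. Section 7.4.1 sends every delayed participant to Section 7.4.3 before dosing resumes, and Sections 7.4.2 and 8.1.3 repeat the pointer. Section 7.4.3 asks for the table requirements and then adds its own. A site that follows Section 7.4.3 in full satisfies both rules. The table cells also leave out general conditions that plainly apply, such as the 10 mg prednisone limit for all AEs, so silence in one cell proves little. Finally, the table requires no delay for Grade 1 pneumonitis arising on its own, which limits the safety weight of the gap.

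Most of this stands. The cumulative, stricter reading is the better one, and a reader who inferred that the protocol has no answer would go too far. What remains is that the cell states a different threshold from the text; it does more than omit a condition. The opening sentence of Section 7.4.3 refers only to the table, and precedence is never stated.

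Three other inferences are tempting and not supported.

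- A reader might infer that the row by itself allows re-dosing on up to 10 mg prednisone. The row is silent on steroids; that limit comes from Section 7.4.3. The unsafe path needs the row and the opening sentence to be read together and the later pulmonary sentences to be missed.
- A reader might count baseline, taper and approval as three separate missing conditions. They are one rule with one exception.
- A reader might infer that pneumonitis is the only row out of line. The two catch-all rows share the mismatch for other pulmonary toxicity.

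**Conclusion.** The inconsistency is real and minor. It lies in the current operative text, not in an amendment log. It changes the re-dosing decision for one kind of participant: no pneumonitis at baseline, Grade 1 persisting after a Grade 2 drug-related event, and the exception in Section 7.4.3 not met. The analogous case arises under the two catch-all rows for other pulmonary toxicity.

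The documents give no pneumonitis rate, so the number of participants affected cannot be estimated. A reader might infer consequences for the PK endpoints or for comparisons between parts of the study; nothing in the documents supports that.

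One limit applies. Section 7.4.3 also refers to Appendix 6, and the pulmonary algorithm figure there is not shown. Whether it repeats the taper and approval conditions could not be checked. Appendix 6 describes itself as guidance.

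**What to change.** Two wording changes.

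1. Replace the resume text in the Grade 2 pneumonitis cell with the rule of Section 7.4.3: *resume at baseline; persistent Grade 1 only once a steroid taper of at least 1 month has been completed, and with Medical Monitor discussion and approval.*
2. End the opening sentence of Section 7.4.3 with *the requirements per Table 7.4.1-1 and the conditions below*. This settles precedence and also covers the two catch-all rows, which then need no edit.

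Neither change adds a requirement, because Section 7.4.3 already contains the stricter conditions. Design, data collection and analysis are unchanged. The downside is a possibly longer delay for a few participants who would otherwise have restarted at Grade 1. Section 8.1.1 already exempts prolonged steroid tapers for drug-related events from the 6-week discontinuation rule, so the taper itself would not force anyone off treatment. The change can go into the next amendment, or into an administrative letter, in which case Appendix 2 requires investigators to inform their IRB or IEC.

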7.4.4 Management Algorithms for Immuno-Oncology Agents

7.4.4.1 Program Safety Management Algorithms

Immuno-oncology (IO) agents are associated with AEs that can differ in severity and duration than AEs caused by other therapeutic classes. Nivolumab is considered as an IO agent and the

management algorithms in [Appendix 6](#) provide guidance on assessing and managing the following groups of AEs:

- Gastrointestinal
- Renal
- Pulmonary
- Hepatic
- Endocrinopathy
- Skin
- Neurological
- Myocarditis

Appendix 6 provides the management algorithms for AEs in the above categories. Note that the program management algorithm for Hepatic AEs in participants with HCC has been modified for this protocol (see the following Section 7.4.4.2).

7.4.4.2 *Recommendations for Management of Hepatic Events in Nivolumab Participants with HCC*

The nivolumab program has developed a standardized approach for the management of hepatic events based on cumulative data across the program in participants with normal hepatic function.

Across most nivolumab studies, the eligibility criteria for inclusion are based on a maximum AST or ALT $< 3 \times$ ULN; therefore, only participants with normal to Grade 1 liver function tests have been enrolled. Participants with advanced HCC generally have underlying cirrhosis with decreased hepatic function. They may also have a concomitant chronic viral infection. For CA2098KX, the upper limits for inclusion were therefore adjusted to account for baseline liver dysfunction. Participants with AST or ALT elevations within the CTCAE Grade 2 range are eligible for inclusion. In contrast, the majority of participants included in prior nivolumab studies have had no higher than a CTCAE Grade 1 AST or ALT elevation. Criteria for dose delay, resumption, & discontinuation are in Section 7.4.2, [Section 7.4.3](#), and [Section 8.1.1](#). The tumor-specific approach for the management of hepatic events is as follows:

- If AST or ALT levels do not improve with a dose delay of 3-5 days or if the levels worsen, initiate steroid therapy at 0.5-2 mg/kg/day methylprednisolone or oral equivalent.
- For ALT or AST levels $> 8 \times$ ULN, initiate steroid therapy promptly at 1-2 mg/kg/day methylprednisolone or oral equivalent.
- For all participants initiating steroids, consult the BMS Medical Monitor within 24 hours after initiation of steroids. Gastroenterology consult is recommended.

- If AST or ALT levels do not improve within 3-5 days or the levels worsen after the start of steroid therapy, discuss with the BMS Medical Monitor the possibility of adding mycophenolate mofetil at 1 g BID.
 - If no response to mycophenolate mofetil, consider treatment with tacrolimus or other immunosuppressants per local guidelines and in discussion with the BMS Medical Monitor. Avoid infliximab due to potential risk of liver failure.
- Tapering of steroids can start once AST or ALT levels have declined by 1 CTCAE grade. Taper steroids slowly over no less than 1 month.

As outlined in [Section 7.4.3](#), nivolumab therapy may resume when AST or ALT have returned to near baseline unless the criteria for permanent discontinuation are reached ([Section 8.1.1](#)).

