Across most nivolumab studies, the eligibility criteria for inclusion are based on a maximum AST or ALT $< 3 \times$ ULN; therefore, only participants with normal to Grade 1 liver function tests have been enrolled. Participants with advanced HCC generally have underlying cirrhosis with decreased hepatic function. They may also have a concomitant chronic viral infection. For CA2098KX, the upper limits for inclusion were therefore adjusted to account for baseline liver dysfunction. Participants with AST or ALT elevations within the CTCAE Grade 2 range are eligible for inclusion. In contrast, the majority of participants included in prior nivolumab studies have had no higher than a CTCAE Grade 1 AST or ALT elevation. Criteria for dose delay, resumption, & discontinuation are in [Section 7.4.2](#), [Section 7.4.3](#), and [Section 8.1.1](#). The tumor-specific approach for the management of hepatic events is as follows:

- If AST or ALT levels do not improve with a dose delay of 3-5 days or if the levels worsen, initiate steroid therapy at 0.5-2 mg/kg/day methylprednisolone or oral equivalent.
- For ALT or AST levels $> 8 \times$ ULN, initiate steroid therapy promptly at 1-2 mg/kg/day methylprednisolone or oral equivalent.
- For all participants initiating steroids, consult the BMS Medical Monitor within 24 hours after initiation of steroids. Gastroenterology consult is recommended.
- If AST or ALT levels do not improve within 3-5 days or the levels worsen after the start of steroid therapy, discuss with the BMS Medical Monitor the possibility of adding mycophenolate mofetil at 1 g BID.
 - If no response to mycophenolate mofetil, consider treatment with tacrolimus or other immuno-suppressants per local guidelines and in discussion with the BMS Medical Monitor. Avoid infliximab due to potential risk of liver failure.
- Tapering of steroids can start once AST or ALT levels have declined by 1 CTCAE grade. Taper steroids slowly over no less than 1 month.

As outlined in Section 7.4.3, nivolumab therapy may resume when AST or ALT have returned to near baseline unless the criteria for permanent discontinuation are reached (Section 8.1.1).

Endocrinopathy Adverse Event Management Algorithm

Rule out non-inflammatory causes. If non-inflammatory cause, treat accordingly and continue I-O therapy.
Consider visual field testing, endocrinology consultation, and imaging.

[figure not shown]

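### The restart rule for HCC participants after a drug-related hepatic elevation is worded differently in Section 7.4.3 than in Section 7.4.4.2 and Appendix 6, which claim to restate it

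*Combined protocol and SAP*

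**What the plan says.** Three places in the protocol tell a site when an HCC participant may restart after a hepatic delay.

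- Section 7.4.3, under the HCC bullet: participants delayed for "drug-related elevations in AST, ALT, or total bilirubin may resume treatment when these values have returned to their baseline CTCAE Grade or normal", provided no permanent-discontinuation criterion is met.
- Section 7.4.4.2, last sentence: "nivolumab therapy may resume when AST or ALT have returned to near baseline", again subject to the permanent-discontinuation criteria. The sentence opens by attributing this to Section 7.4.3.
- Appendix 6, hepatic algorithm modified for HCC: "As outlined in Section 7.4.3, nivolumab therapy may resume when AST or ALT have returned to near baseline".

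Section 7.4.4.2 also says which sections govern: "Criteria for dose delay, resumption, & discontinuation are in Section 7.4.2", and the list goes on to 7.4.3 and 8.1.1. Appendix 6 repeats that statement. The hepatic rows of Table 7.4.1-1 are labelled as applying to non-HCC participants and send HCC participants to 7.4.2 and 7.4.3. For the lower non-HCC row the table says "Dosing may resume when laboratory values return to baseline". Above 5 x ULN for AST or ALT it expects discontinuation in most cases, and otherwise Medical Monitor approval before restart.

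The closing paragraph of 7.4.3 is not limited to HCC. It ends "For hepatic AE management, see" Section 7.4.4.2.

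**The concern.** Two sentences present themselves as a summary of Section 7.4.3 and say something else. They differ from it in the standard (a CTCAE grade against an undefined nearness to baseline) and in the analytes (bilirubin named in one, absent from the other). The conjunction adds to this, because AST or ALT can be read as either one being enough.

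The rule decides whether a participant is dosed again after hepatotoxicity, in a population with compromised liver function at entry. HCC is eligible in all of Parts A to E. Appendix 6 is the text a site is likely to have open when managing such an event. If sites work from different sentences, similar participants may be re-dosed on different criteria.

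The unqualified pointer at the end of 7.4.3 adds a smaller problem. A reader managing a hepatic event in a participant without HCC is sent to a section written for HCC only.

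**Working it through.** The protocol gives no figure to reproduce. The check sets the wordings side by side and asks, case by case, which is more permissive.

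**Inputs**

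- AST/ALT grade bands: not stated in the protocol. Section 7.4.4.2 equates an entry limit below 3 x ULN in other nivolumab studies with normal to Grade 1, so I take the top of Grade 1 as about 3 x ULN. Section 6.1 admits HCC participants up to 5 x ULN, which 7.4.4.2 describes as the Grade 2 range, so I take the top of Grade 2 as about 5 x ULN. Both are inferences and treat grades as fixed multiples of ULN.
- HCC delay triggers (7.4.2): any Grade 3 drug-related laboratory abnormality, with only asymptomatic amylase or lipase changes excepted. Bilirubin can therefore trigger a delay.
- HCC permanent discontinuation for bilirubin (8.1.1): above 5 x ULN if normal at entry, above 8 x ULN if raised at entry.

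**Case 1: abnormal AST or ALT at baseline.** Under 7.4.3 the highest value at which restart is allowed is the top of the baseline grade band. The ratio to baseline is (top of band) / (baseline value):

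| Baseline (x ULN) | Top of band (x ULN) | Ratio |
|---|---|---|
| 1.2 | 3.0 | 3.0 / 1.2 = 2.5 |
| 2.0 | 3.0 | 3.0 / 2.0 = 1.5 |
| 3.5 | 5.0 | 5.0 / 3.5 = 1.4 |

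A value 2.5 times baseline meets 7.4.3 but may well not count as near baseline. Here 7.4.3 can be the more permissive text.

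**Case 2: normal AST and ALT at baseline.** Under 7.4.3 the baseline grade and normal are the same thing, so the value must be normal. The other wording could be read to admit a value slightly above ULN. Here 7.4.4.2 and Appendix 6 may be the more permissive.

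**Case 3: delay triggered by bilirubin.** Under 7.4.3 bilirubin must return to its baseline grade or normal. The sentence in 7.4.4.2 and Appendix 6 asks only about AST or ALT, and its only guard is the permanent-discontinuation criteria. Read alone, it lets dosing restart with bilirubin anywhere up to 5 x ULN (normal at entry) or 8 x ULN (raised at entry). Here it is clearly the more permissive.

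**The pointer.** Section 7.4.4.2 is headed for participants with HCC, and 7.4.4.1 describes it as the HCC modification of the programme algorithm. The opening paragraph of 7.4.3 requires Table 7.4.1-1 to be met, and that table holds the non-HCC hepatic restart rule. The pointer concerns management and is not itself a restart criterion, so non-HCC restart stays where the table puts it.

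**The case against.** The strongest reply is that the protocol says which text governs. Section 7.4.4.2 places the resumption criteria in 7.4.2, 7.4.3 and 8.1.1, its disputed sentence cites 7.4.3, and Table 7.4.1-1 sends HCC participants to 7.4.2 and 7.4.3. Section 7.4.4.2 is titled as recommendations and Appendix 6 calls itself guidance. On this view the near-baseline sentence is a loose paraphrase, and its silence on bilirubin only reflects a section whose steps are driven by AST and ALT. A site that follows the citation finds bilirubin named in 7.4.3. A site that also re-applies 7.4.2 would still hold the dose while a drug-related bilirubin abnormality is at Grade 3.

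Much of this stands. It shows that 7.4.3 is the intended source, and it narrows the bilirubin gap for anyone who reads all the sections together. It does not remove the inconsistency: a sentence that cites a rule and misstates it is still an instruction a site can act on, and it appears twice.

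Two stronger readings are tempting, and the documents do not support them. A reader might infer that 7.4.4.2 is simply the looser text, but Case 1 shows the reverse for an abnormal AST or ALT baseline. A reader might also infer from the pointer that all hepatic events, HCC or not, fall under the near-baseline rule. No text puts a non-HCC participant there.

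**Conclusion.** The inconsistency is real and limited to HCC participants. Section 7.4.3, which the other texts name as the source, and the two passages that claim to restate it give different standards and cover different analytes. The direction of the difference depends on the baseline and the analyte: near-baseline is more permissive for bilirubin and possibly for a normal baseline, while baseline grade can be more permissive for AST or ALT when baseline is abnormal. The ratios of 1.4 to 2.5 rest on the inferred grade bands. The textual conflict does not.

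The unqualified pointer in 7.4.3 is a separate scope error in a cross-reference and leaves the non-HCC rule intact.

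The practical effect cannot be sized. The number of HCC participants is not given. A reader might infer that the choice of wording moves participants across the 6-week delay limit and so changes the count of AEs leading to discontinuation. The documents give no rate of AST or ALT recovery from which to show this, and delays for prolonged steroid tapers are exempt from that limit. I would not claim an effect on that descriptive endpoint. Sample size, alpha and power are not touched. The point merits correction because it concerns re-dosing after liver toxicity and is cheap to repair. Which threshold is right is outside this review.

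**What to change.** Reconcile Section 7.4.3, Section 7.4.4.2 and the HCC text in Appendix 6.

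1. State one restart criterion for HCC participants, once, in 7.4.3, and say how AST, ALT and total bilirubin each count, including whether every elevated analyte must meet it.
2. Replace the closing sentence of 7.4.4.2 and of the Appendix 6 HCC text with a cross-reference to 7.4.3, so that no second wording remains.
3. Limit the closing pointer in 7.4.3 to HCC participants.

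The sponsor's clinical team decides the threshold. The cost is wording in three places at the next amendment, with no new data, visits or analyses.
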